1 STUDY INFORMATION

The aim of the present Proof of Concept Phase II clinical study is to:

- Demonstrate the efficacy of a continuous daily dosing for 28 days of ivermectin for the prevention of COVID-19 infection in humans,
- Consolidate current knowledge on the ivermectin safety profile,
- Collect data on potential ivermectin effects on COVID-19 clinical outcomes.

1.1 Primary objective

The primary objective of this study is to assess the efficacy of ivermectin compared to placebo in the prevention of laboratory-confirmed COVID-19 infection.

1.2 Secondary objectives

The following secondary objectives will be investigated:

- To assess the efficacy of ivermectin on Time to RT-PCR positive testing.
- To assess the efficacy of ivermectin on the occurrence of severe COVID-19 symptoms.
- To assess the efficacy of ivermectin on Time to first COVID-19 related clinical events.
- To assess the efficacy of ivermectin on the rate of COVID-19 related hospitalisations.
- To assess the efficacy of ivermectin on the rate of COVID-19 related mortality.
- To assess the safety and tolerability of ivermectin given for a period of 28 days.

1.3 Study design

This is a randomised, double blind, parallel-group, placebo-controlled, multicentric Phase II clinical trial evaluating the efficacy and safety of ivermectin tablets in the prevention of COVID-19 infection.

If all eligibility criteria are met, the participant will be randomised, and a loading treatment dose will be administered.

Participants will be assigned in a 1:1 ratio to receive oral daily treatment with either ivermectin or placebo. Randomisation will be performed stratified by country.

The study requires two visits to the study center, on Day 1 and Day 28, the first and last days of treatment. In addition, there will be 3 remote visits (day 4, day 7 and day 10) that can be conducted by telephone.

The treatment period lasts for 28 days in total, followed by a 28-day follow-up period, and there is a 2-day window period for visits. Therefore, total study duration for each participant is up to 58 days.

Ivermectin will be supplied as 3 mg tablets and will be administered orally, under fasting conditions, as follows: 200 ug/kg as the loading dose on Day 1 and then 100 ug/kg/day for

Statistical Analysis Plan	Version 1.0		Page 7 of 25
Sponsor	MedinCell	Protocol No	mdc-TTG-CT-002

27 days. Control participants will receive placebo tablets, the number of tablets to be taken will match the number of IVM tablets taken by the active participants in the same body weight range.

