I understand that the information/technology contained in this protocol is proprietary and may not be disclosed to any other party, in any form, without prior authorisation from the trial sponsor except to the extent necessary to obtain informed consent from potential trial participants.

PROTOCOL SYNOPSIS

Title:	A multicentre randomised, Double-Blind, Placebo-controlled, S tudy to evaluate the effic A cy and safety of oral IVE rmectin tablets in the prevention of COVID-19 (the SAIVE Trial)		
Protocol Number:	mdc-TTG-CT-002		
Study Phase:	II		
Sponsor:	MedinCell SA		
Coordinating Investigator:	[name]		
Study Objectives:	To assess the efficacy of ivermectin compared to placebo in the prevention of laboratory-confirmed COVID-19 infection.		
	 Secondary objectives: To assess the efficacy of ivermectin on Time to RT-PCR positive testing. To assess the efficacy of ivermectin on the occurence of severe COVID-19 symptoms. To assess the efficacy of ivermectin on Time to first COVID-19 related clinical events. To assess the efficacy of ivermectin on the rate of COVID-19 related hospitalisations. To assess the efficacy of ivermectin on the rate of COVID-19 related mortality. To assess the safety and tolerability of ivermectin given for a period of 28 days. 		
Study Design:	This is a randomised, double blind, placebo-controlled, multicen Phase II clinical trial evaluating the efficacy and safety of ivermed tablets in the prevention of COVID-19 infection. If a person tests positive for SARS-CoV-2 (index case), they obtain details of this study, in leaflet form, at the clinic or laborat where they received their positive result. The index case can the provide details of this study to their close contacts. A close contact is defined as: • Anyone who lives in the same household as another per who has tested positive for COVID-19. • Anyone who has had any of the following types of contact with someone who has tested positive for COVID-19: • Face-to-face contact including being coughed or having a face-to-face conversation within metre • Been within one metre for one minute or lon without face-to-face contact • Been within 2 metres for more than 15 minueither as a one-off contact, or cumulatively over 24-hour period • A person may also be considered a close contact they have travelled in the same vehicle or plant a person who has tested positive for COVID-19.		

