The number/frequency of participants with TEAEs, related TEAEs, PTAE, the number/frequency of participants with related PTAEs, SAEs and CTCAE grade 3 or more will be displayed by system organ class and preferred term according to MedDRA classification. The frequency of participants with at least one TEAE, PTAE, related PTAE, SAE and/or AE of CTAE grade 3 or more will be compared between treatment groups using a chi-squared test or a Fisher exact test.

Table 1: Schedule of Assessments

	Pre Screening D-1 or D1*	Screening & Randomisation	On-treatment period (i)				EOS (J)
		D1	D4 (±1 day)	D7 (±1 day)	D10 (±1 day)	EOT-D28** (+2 days)	D56 (±2 days)
	Remote	On-site Visit***	Remote	Remote	Remote	On-site Visit***	Remote
Study participation suitability questionnaire (a)	X						
ICF signature (b)		X					
Demographics		X					
Medical history		X					
I/C criteria		X					
Treatment dispensation		X					
Treatment administration (c)						-	
RT-PCR test (d)		X	X	X	X	X	
Antigen test (e)		X					
Serology (f)		X				X	X
NEWS-2 scale		X			X	X	
COVID-19 WHO scale		X			X	X	
Laboratory tests (g)		X				X	X
Urine pregnancy test (g)		X				X	X
Randomisation		X					
Participant diary (i)						•	
ECG		X				X	
Vital signs		X			X	X	
Adverse Events			· -				
Concomitant medication							

Clinical Protocol

- * Pre-Screening corresponds to the time frame when the first positive case is detected in the cluster within 5 days prior to screening. The study is immediately proposed to the exposed cluster members who might potentially meet the eligibility criteria (Note: only one member in the same household will be enrolled).
- ** Preferred on-site visit but can be performed remotely according to the investigator's opinion.
- *** In case of on-site visit, participants should only use private transport. Moreover, a specific room for participants has to be available and restricted to participants in order to limit their contact with patients.
- a) Participants will be questioned about their close contact to the COVID-19 index case, their interest in participating in the study, and will be given information about the study (note that full eligibility inclusion/exclusion criteria will be confirmed once the participant has signed an ICF).
- (b) ICF signature for the participant and the index case to collect information regarding his/her SARS-CoV-2 RT-PCR test results,

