4.6 Efficacy

4.6.1 Primary endpoint

The primary endpoint is the proportion of laboratory-confirmed COVID-19 infections between baseline and Day 28. Frequency tables will be provided, and individual results will be listed.

For missing results of the primary endpoint, the multiple imputation (MI) method will be used. MI is performed using 3 general steps: imputation, analysis, and pooling. A total of 10 multiple imputations will be generated using a fully conditional specification (FCS) regression. This method conditions on observed values of the primary outcome measured at other time points (including baseline measurements) and possible other covariates that are related to the missing data pattern and/or primary endpoint. Furthermore, imputations will be performed in each treatment group separately and, if applicable, by stratification factor. The statistical model will be applied to each imputed dataset separately. The estimated parameters from the models will then be pooled using Rubin's combining rules. It should be noted that these combination rules rely on the assumption that the estimated

Statistical Analysis Plan	Version 1.0		Page 14 of 25
Sponsor	MedinCell	Protocol No	mdc-TTG-CT-002

statistics are approximately normally distributed, which may not be the case for the underlying data. Normalizing transformations will then be used on the estimated statistics prior to applying Rubin's rules.

The comparison between the two treatment groups of the proportion of participants will be performed using the Cochran Mantel Haenszel (CMH) chi-squared test. Odds-ratio, relative risk and risk differences and corresponding 95% CI will be reported. Country will be used as a stratification factor. In case the study was only performed in one country, the Chi-squared/Fisher's exact test will be used.

This analysis will be performed based on the mFAS and PP population using the planned treatment

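### The primary test is stratified by country only; adding household versus other contact as a stratum would be a cheap gain in efficiency, not the repair of an error

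*SAP*

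**What the plan says.** The close-contact definition in the protocol synopsis (Study Design) is broad. It begins with household members ("Anyone who lives in the same household as another"), goes on to one minute or more within one metre, and allows that people may count because "they have travelled in the same vehicle" or plane. The inclusion criteria require only a close contact within 5 days, so all these people can enter one modified full analysis set (SAP 3.4). Footnote a to the protocol's Schedule of Assessments says of pre-screening: "Participants will be questioned about their close contact to the COVID-19 index case".

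SAP 1.3 states "Randomisation will be performed stratified by country". For the primary CMH test, SAP 4.6.1 states "Country will be used as a stratification factor", with a plain chi-squared or Fisher test if only one country takes part. The protocol's supporting logistic regression has treatment and country. The exploratory model in SAP 4.6.3 gives sex, age, BMI and variant as examples. None of these names contact type.

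The 54% placebo rate (protocol synopsis and SAP 1.4) comes from a study of transmission in households.

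**The concern.** Sharing a home with an infected person and passing a minute near one are different exposures, so contact type is a plausible strong predictor of the primary outcome. A test that pools the two groups carries the between-group difference in risk as noise, and a chance difference between arms in the share of household contacts feeds into the estimate. Stratifying the test on a strong baseline predictor removes most of that noise at little cost. What is at stake is some power and precision in the primary comparison, and a clearer reading of the result in household contacts, the setting behind the planning rate.

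**Working it through.** **The plan's own figures.** With 54% versus 34%, two-sided 5% and 90% power, the Casagrande-Pike formula gives 137.2, rounded up to 138 per arm. Then 138 / 0.70 = 197.1, rounded up to 198 per arm, or 396 in total. The odds ratio is (0.54/0.46) / (0.34/0.66) = 2.28. All three agree with the documents.

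**Inputs for the check.** From the documents: 138 evaluable per arm, 54%, odds ratio 2.28, two-sided 5%. Assumed, because the documents do not give them: household share, non-household placebo risk (5% to 30%), the same odds ratio in both contact types, one country and complete data.

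**What a mixture does (70% household, non-household risk 10%).**
- Non-household ivermectin odds: (0.10/0.90) / 2.28 = 0.0487, so the risk is 0.0487/1.0487 = 4.6%.
- Pooled placebo risk: 0.7 × 0.54 + 0.3 × 0.10 = 40.8%.
- Pooled ivermectin risk: 0.7 × 0.34 + 0.3 × 0.046 = 25.2%.
- Expected difference: 15.6 points instead of 20.

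**Power.** 40,000 simulated trials per scenario, Mantel-Haenszel chi-squared with 1 df, without and then with contact type as a stratum:

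| Household share | Non-household risk | Without | With | Gain (points) |
|---|---|---|---|---|
| 70% | 5% | 75.7% | 82.6% | 6.9 |
| 70% | 10% | 79.1% | 84.4% | 5.3 |
| 70% | 20% | 84.8% | 87.3% | 2.5 |
| 70% | 30% | 88.4% | 89.4% | 1.0 |
| 50% | 5% | 60.4% | 71.9% | 11.5 |
| 50% | 10% | 67.7% | 76.0% | 8.3 |
| 50% | 20% | 78.7% | 83.0% | 4.3 |
| 50% | 30% | 85.6% | 87.3% | 1.7 |

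Simulation error is about a quarter of a point per power figure (for example √(0.6 × 0.4 / 40,000) = 0.24 points). A repeat with 200,000 runs put the largest gain at 11.0. At 90% household the gain is 0.6 to 2.0 points.

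**Other checks.**
- Type I error was 0.047 to 0.051 in the mixed scenarios, with either test.
- If non-household risk is also 54%, power is 91.8% without and 92.0% with the stratum, so nothing is lost.
- With five equal countries crossed with contact type (10 strata, 70% household, 10% risk), power still rises from 78.9% to 83.8%.
- Forcing balance on contact type at allocation changes power by only about 1 point beyond stratifying the analysis.

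**Chance imbalance at 70% household.** The SD of the between-arm difference in household share is √(2 × 0.7 × 0.3 / 138) = 5.5 points. With risks of 54% and 10%, one SD moves the unadjusted risk difference by 0.055 × 44 = 2.4 points.

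**The case against.** The strongest reply is that this is a preference about efficiency. The plan analyses by its randomisation stratum, which is coherent, and chance imbalance in an unadjusted covariate is already covered by the test's error rate. That stands. A reader might infer that the primary test is invalid or biased, and the documents and the simulation do not support that.

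The gain also rests on two inputs the documents lack. The recruitment route may favour closer contacts: the index case passes on the study details, and the participant must bring the index case's signed consent and PCR result. Strangers exposed for a minute may seldom manage this, which makes the scenarios with very low non-household risk less representative. This stands as a reason for caution about size, although the documents do not give the actual mix.

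A reader might infer that the trial could not say whether an effect holds in household contacts. That is too strong. The factor list in SAP 4.6.3 is open-ended, and only part of the protocol and SAP is available to read. What can be said is that contact type is not named.

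Two practical objections also stand. Being asked about contact does not show that contact type is coded and kept as trial data. And SAP 4.6.1 imputes within treatment group and, if applicable, by stratification factor, so a new stratum could leave sparse imputation cells. With an assumed three equal countries and 30% non-household, 200 × 0.30 / 3 = 20 people per cell, and at 5% risk about one event.

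**Conclusion.** The point holds as a cheap efficiency improvement and not as an error in the plan. Under the assumptions above, stratifying the primary CMH test by contact type as well as country gains about 1 to 7 points of power at 70% household contacts, 2 to 11 at 50% and 1 to 2 at 90%. The gain is large only if non-household risk is low and the non-household share is sizeable. No simulated scenario showed a material loss.

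A reader might infer that the stratum would repair the trial's power. It would not: every stratified figure in the table is below 90%. The larger part of any shortfall comes from a pooled event rate below the household-based 54%, which is a separate matter. Severity: consider.

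**What to change.** Before unblinding:

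1. Confirm that contact type at entry (household versus other) is recorded as a coded baseline field, and add the field if it is not.
2. In SAP 4.6.1, stratify the primary CMH test by country and contact type. If only one country takes part, stratify by contact type alone in place of the plain chi-squared or Fisher test.
3. In the multiple imputation, enter contact type as a covariate in the fully conditional specification model and do not split the imputation further by it, so that cells do not become sparse.
4. Report the risk difference within each contact type descriptively, and name contact type in the SAP 4.6.3 model.

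The randomisation need not change. SAP 2.1 already provides for an amendment before database lock and unblinding. The cost is SAP wording and one data field, which may need new capture or retrospective coding, plus smaller strata in the primary test. The CMH test tolerated the smaller strata in the five-country check.

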1.4 Planned sample size

The sample size was calculated to compare the proportion of participants who become positive to SARS-CoV-2 RT-PCR within 1 month after randomisation between the two groups: Placebo group and ivermectin group. The assumptions are based on results of a study assessing the transmission of SARS-CoV-2 infections in households carried out in the US between April and September 2020. Thus it is expected that the proportion of participants becoming infected in the placebo group is 54% or higher (Grijalva et al, 2020). Furthermore, a reduction by 20% is expected in the ivermectin group (OR=2.28).

When requiring a power of 90% (1- β) and a significance level of 5% (α), then according to the Casagrande & Pike formula the required sample size to detect such difference with a test of comparison of two proportions is equal to 138 participants per treatment arm (Casagrande et al, 1978).

A total of 396 participants (198 per arm), rounded up to 400 participants (200 per arm) is required to account for an estimated rate of randomised participants who won't be valued for the primary analysis of 30%.

[figure not shown]

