Inclusion Criteria:	 Individuals who meet all of the following criteria are eligible to participate in the study: Age between 18 and 65 years, inclusive. Body weight >45 kg. Body Mass Index >18.5. Close contact with a person who has a PCR-confirmed SARS-CoV-2 infection within 5 days before screening. Only one member in the same household will be enrolled. Participants must be able to give informed consent and comply with the study's scheduled events/visits and study assessments. SARS-CoV-2 positive index case must be able to give consent to enable collection of the documented positive PCR test. Female participants of childbearing potential must use a highly effective method of contraception for the duration of the trial. Their male partners should also use a contraception method (i.e condom) unless vasectomized. (Refer to section 4.5 Contraception Requirements). Male participants must use a contraception method (i.e condom) for the duration of the trial, unless vasectomized. Their female partners, if they are of childbearing potential, must use a highly effective method of contraception. (Refer to section 4.5 Contraception Requirements). 			

Exclusion Criteria:	Individuals who meet any of the following criteria are not eligible to			
	participate in the study:			
	1. Pregnant or breast-feeding.			
	2. Participants who have been administered COVID-19 vaccine			
	prior to the inclusion or have a planned vaccination during			
	the duration of the study.			
	3. A positive COVID-19 result (PCR or antigen test) within 8 days of screening.			
	4. Presence of typical COVID-19 symptoms (fever >38°C,			
	SpO2 below 93%, dyspnoea, difficulty breathing, chills,			
	repeated shaking with chills, ageusia, anosmia, cough,			
	myalgia, headache) in the past 48 hours prior to screening.			
	5. Presence of a known uncontrolled/unstable clinically			
	significant medical condition, considered by the investigator			
	as incompatible with study participation.			
	6. Known history of HIV, HBV and/or HCV.7. Hypersensitivity to any component of ivermectin.			
	J1 J J 1			
	8. Participants who have been administered ivermectin within 30 days prior to screening.			
	9. Participation in another interventional trial within the last 30			
	days or 5 half-lives of the IMP of the other trial, whichever			
	comes first.			
	10. Having undergone extensive bowel resection which may			
	alter ivermectin absorption.			
	11. Participants with gastrointestinal erosions and ulcers (e.g.			

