Terminology Criteria for Adverse Events (CTCAE version 5.0). **Statistical Methods:** Sample size: Sample size was calculated to compare the proportion of participants who become positive to SARS-CoV-2 RT-PCR within 1 month after randomisation between the two groups: Placebo group and experimental group receiving ivermectin up to D28. Based on a study assessing the transmission of SARS-CoV-2 infections in households carried out in the US between April and September 2020, the proportion of randomised participants becoming infected in the placebo group is estimated to be 54% (Grijalva et al, 2020).. A difference of 20% is expected between the two groups (OR=2.28). With a power of 90% (1- β) and a significance level of 5% (α), according to the Casagrande & Pike formula the required sample size to detect such difference with a test of comparison of two proportions is equal to 138 participants per arm (Casagrande et al, 1978). A total of 396 participants (198 per arm), rounded up to 400 participants (200 per arm) is required to account for the primary analysis. This sample size also accounts for an estimated dropout rate of 30%. Primary endpoint analysis: The comparison of proportion of participants who were tested positive for SARS-CoV-2 up to D28: placebo group versus ivermectin group, will be performed using the Cochran-Mantel Haenszel (CMH) chi-squared test at the two-sided 0.05 level. Twosided 95% confidence intervals (95% CI) for the proportion differences between groups will be provided. Odds-ratio and corresponding 95% CI will also be reported. The primary endpoint will also be analysed using a logistic regression with treatment group and country as a covariate. Moreover, the analysis of the primary endpoint will be performed for the PP population.

Clinical Protocol

Safety analysis:

Safety will be pooled analyses for the Safety set from all centres and countries. Placebo and ivermectin groups will be compared.

All adverse events (AEs) will be coded according to coding dictionaries (MedDRA, applicable version) and summarised at System Organ Class (SOC) and Preferred Term (PT) levels. AEs will be classified according to period of occurrence: pre-treatment AEs, treatment-emergent AEs (TEAEs) and post-treatment AEs (PTAEs). AE reporting will focus on TEAEs and PTAEs. Incidence of TEAEs and PTEAEs will be summarised and detailed by seriousness, intensity, action taken with the study medication, other action taken and relationship to study treatment.

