3.4 Modified Full Analysis Set

Modified FAS (mFAS) includes all FAS participants with a confirmed negative SARS-CoV-2 RT-PCR test at baseline.

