3.5 Per-protocol Set

The Per-Protocol Set (PPS) is a subset of participants in the mFAS who did not present major deviations from the trial protocol.

The primary efficacy endpoint will be analysed using the mFAS and the PP set. The PP analysis will be considered as a sensitivity analysis.

Secondary efficacy endpoints will be analysed using the FAS or mFAS and PP set.

In case of dispensation/randomisation major error (i.e. the participant did not receive the treatment planned by the randomisation), in agreement with the intention-to-treat (ITT) principle, participants in FAS and mFAS analyses will be analysed in the group planned by the randomisation and not "as treated". As treated analyses will be performed as sensitivity analyses only if the frequency of major dispensation/randomisation error is greater than 10%.

The safety set will be used for safety analyses. In case of dispensation/randomisation major error the safety analyses will be performed "as treated", according to the real treatment received by the participant.

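### Does a 54% placebo rate taken from a household study undermine the stated 90% power for the baseline-negative primary analysis set?

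*SAP*

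**What the plan says.** The protocol synopsis (Statistical Methods) bases the sample size on a US household study from April to September 2020 and says that "the proportion of randomised participants becoming infected in the placebo group is estimated to be 54" per cent. SAP section 1.4 uses the same source but treats the figure as a floor: "Thus it is expected that the proportion of participants becoming infected in the placebo group is 54% or higher".

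The effect is worded in two ways. The protocol has "A difference of 20% is expected between the two groups (OR=2.28"; the SAP has "a reduction by 20% is expected in the ivermectin group (OR=2.28". Both documents then give 90% power, 5% significance, the Casagrande & Pike formula, 138 per arm, 198 per arm after a 30% allowance, and 400 in total. The protocol calls the 30% dropout. The SAP applies it to all randomised participants who will not count in the primary analysis.

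On the population, SAP section 3.5 states: "The primary efficacy endpoint will be analysed using the mFAS and the PP set". Section 3.4 defines that set: "Modified FAS (mFAS) includes all FAS participants with a confirmed negative SARS-CoV-2 RT-PCR test at baseline". The protocol's definition of a close contact starts with household members and then adds "Anyone who has had any of the following types of contact with someone who has tested positive for COVID-19", with shared travel also allowed. Exclusion criterion 3 removes anyone with "A positive COVID-19 result (PCR or antigen test) within 8 days of screening", and criterion 4 removes those with typical symptoms in the previous 48 hours.

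**The concern.** The planning rate and the primary analysis seem to describe different people. If the household study counted contacts who were already infected when first tested, part of its 54% would be removed here by the antigen screen and the Day 1 RT-PCR. Brief or non-household contact could also carry less risk than living with a case. Both would push the placebo rate in the mFAS below 54%, and nothing in the text supports treating 54% as a lower bound. The 30% allowance replaces lost participants but does not adjust the rate.

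The SAP's wording of the effect can also be read as a relative cut of one fifth, for which the trial would be far too small.

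At stake is how a null result is read. If the real power was well under 90%, failure to reject would say less against ivermectin than the plan implies.

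**Working it through.** **Inputs** (protocol synopsis, Statistical Methods; SAP 1.4): placebo rate p = 0.54; ivermectin rate q = 0.34; d = p − q = 0.20; mean rate m = 0.44; two-sided 5% (z = 1.960); 90% power (z = 1.2816).

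**1. The plan's own figure.** Odds ratio = (0.54/0.46)/(0.34/0.66) = 2.279.

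A = [1.960·√(2·0.44·0.56) + 1.2816·√(0.54·0.46 + 0.34·0.66)]² = (1.376 + 0.881)² = 5.094.

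Uncorrected n = A/d² = 5.094/0.04 = 127.4.

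Corrected n = A[1 + √(1 + 4d/A)]²/(4d²) = 137.2, so 138 per arm.

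138/0.70 = 197.1, so 198 per arm; 396 in total, rounded to 400; 200 × 0.70 = 140. Every printed figure reproduces.

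**2. Absolute or relative 20%?** A relative cut gives 54% × 0.8 = 43.2% and an odds ratio of (0.54/0.46)/(0.432/0.568) = 1.54. It would need 467 per arm, and 138 would give 39% power. Both documents print 2.28 and 138, so only the absolute reading fits.

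**3. Power at other placebo rates.** Inverting the corrected formula at n = 138 per arm gives an effective size n′ = (n − 1/d)²/n, and power = Φ{[d√n′ − 1.960√(2m(1−m))]/√(p(1−p) + q(1−q))}.

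Check at 54% vs 34%: n′ = 133²/138 = 128.2; (2.264 − 1.376)/0.688 = 1.292; power 90.2%.

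Example at 40% with the relative risk held: q = 0.40 × 0.34/0.54 = 0.252; d = 0.148; n′ = 124.8; (1.655 − 1.299)/0.655 = 0.544; power 70.7%.

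The placebo rates below 54% are assumptions. Uncorrected power is in brackets.

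| Placebo rate | 20 points held | Odds ratio 2.28 held | Relative risk 0.63 held |
|---|---|---|---|
| 54% | 90% (92%) | 90% (92%) | 90% (92%) |
| 45% | 92% (94%) | 88% (90%) | 79% (82%) |
| 40% | 94% (96%) | 85% (88%) | 71% (75%) |
| 30% | 98% (99%) | 76% (80%) | 52% (58%) |

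With 20 points held, the lowest corrected power at any placebo rate is 89.8%, near 60%. The 90% is therefore not tied to a 54% rate; it is tied to the size of the absolute difference. SAP 4.6.1 specifies a CMH chi-squared test and mentions no continuity correction, so the bracketed values are nearer to the planned test.

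**4. If 54% did include contacts already positive on Day 1.** Let f be their share of all infections. The mFAS rate is then 0.54(1 − f)/(1 − 0.54f): 45% at f = 30% and 37% at f = 50%. The baseline positives removed are 0.54f, that is 16 and 27 percentage points, both inside the 30% allowance. At 140 per arm, corrected power is 80% and 66% with the relative risk held, or 88% and 84% with the odds ratio held. No value of f can be taken from the documents. If the source rate already referred to baseline negatives, this step lowers nothing.

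**The case for a change.** The best case for a change runs as follows. The rate is quoted for randomised participants while the test is run on a narrower set. The SAP hardens an estimate into a floor without a reason. Holding 20 points at a lower rate is not neutral: the relative reduction must rise from 37% at 54% to 44% at 45%, 50% at 40% and 67% at 30%. For a preventive drug, a constant relative effect is at least as natural, and on that scale corrected power falls below 80% once the placebo rate is under about 46%. SAP section 1 aims to demonstrate efficacy, so a null result ought to be interpretable, and better wording would be cheap.

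Some of this stands. The transfer of the household rate is not discussed in the text available, the floor is unexplained, and power does depend on the effect scale.

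The rest does not carry. The direction is unproven: both sample-size statements describe participants turning positive after randomisation, which presents 54% as an incident rate. Exclusion of vaccinated contacts and repeated RT-PCR up to Day 28 could keep the rate up. The 90% is not unconditional, because its rate, difference, odds ratio and significance level stand beside it. The relative-risk scale that yields the lowest figures appears in neither sample-size statement. The SAP's description of the 30% already covers baseline positives in number, and multiple imputation (SAP 4.6.1) may keep evaluable numbers above 140. A null result would be read from the odds ratio, relative risk and risk difference with 95% confidence intervals that section 4.6.1 requires, whatever rate was assumed in planning.

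**Conclusion.** No change to the plan follows. The stated 90% is delivered under the stated inputs (137.2, so 138 per arm; power 90.2%). With the 20-point difference held it stays at about 90% or more at every placebo rate. A material loss needs two assumptions that the documents neither establish nor exclude: an mFAS placebo rate well below 54%, and an effect constant on the relative-risk or odds-ratio scale. Under both, corrected power at 138 per arm would be 71% or 85% at a 40% rate, and 52% or 76% at 30%.

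Rewording the rationale, adding a table of powers or aligning the two descriptions of the 30% would leave the 400 participants, the primary test, the analysis set and the estimates exactly as they are. A blinded look at the pooled infection rate with no action attached would also decide nothing. The two effect wordings are a loose phrase that the printed odds ratio resolves. The unexplained floor and the borrowed household rate are an undiscussed planning assumption, which is worth remembering when the result is read but is not a defect in the analysis.
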